#### 5.2.3. Additional Analyses of the Primary Endpoint

The primary analysis will be repeated under several subgroups. Subgroup analyses include age groups (cutoff based on tripartite), BMI (≤ median vs. > median), and history of use of specific antipsychotic medication (no treatment since screening vs. long-acting injectable treatment vs. oral treatment only).

Additionally, the MMRM analysis of the primary endpoint will be repeated, adding CDSS Baseline score as a covariate. The analysis will be repeated separately with Simpson-Angus Scale (S-AS) Baseline score as a covariate.

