#### 3.3.2. Examination of Patient Subsets

At present no analyses are planned to examine study results within patient subsets.

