#### 5. STATISTICAL METHODS

Descriptive statistical methods will be used to summarize the data from this study, with hypothesis testing performed for selected endpoints. Unless stated otherwise, the term "descriptive statistics" refers to number of patients (n), mean, median, standard deviation (SD), minimum, and maximum for continuous data and frequencies and percentages for categorical data. All data collected during the study will be included in data listings. Unless otherwise noted, the data will be sorted by treatment group, patient number, and by date within each patient number.

The term 'treatment group' refers to the three treatment arms of this study: Placebo, 32 mg MIN-101, and 64 mg MIN-101.

All statistical testing will be two-sided and will be performed using a significance (alpha) level of 0.050 unless stated otherwise.

The statistical analyses will be conducted with the SAS® System version 9.4 or higher. All analyses will be performed using formal verification procedures. Specifically, results will be verified utilizing independent programming prior to issuance of the draft statistical report. All documents will be verified by the lead statistician to ensure accuracy and consistency of analyses.

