#### 5.2. EFFICACY ANALYSIS

The efficacy analyses will be based on the ITT Population, although they will also be performed for the PP population for comparison.

[figure not shown]
All efficacy parameters will be summarized descriptively by treatment arm and visit, as appropriate. All statistical tests will be 2-sided hypothesis tests performed at the 5% level of significance. All confidence intervals will be 2-sided 95% confidence intervals unless stated otherwise.

Additionally, by-visit analyses will be carried out for all efficacy parameters as deemed applicable using the mixed-effects model for repeated measures (MMRM).

Sensitivity analyses will be performed to better understand the impact of missing data and/or imputation of the primary efficacy endpoint, as described in Section 3.3.4.2.

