#### 5.2.2. Primary Efficacy Analysis

As noted in Section 3.3.4, no imputation of data elements will be performed for the primary analysis to be submitted to the US FDA. Pattern-mixture modelling imputation of missing primary endpoint data will be performed before conducting the primary analysis to submit within the EMA dossier. In both approaches, the estimand and analytic approach of using MMRM to evaluate the potential treatment effects is the same, but the data used to analyze the estimand is different between the US FDA and EMA dossiers.

The PANSS Marder NSFS scores and change from Baseline will be summarized by treatment group and study visit. In addition, the trend in change from Baseline in Marder NSFS scores over the series of visit assessments will be presented graphically.

Change from Baseline to Week 12 in the PANSS Marder NSFS score will be analyzed using a MMRM with fixed effects for treatment group (MIN-101 64 mg, MIN-101 32 mg, and placebo), region, visit, and treatment-by-visit interaction, a random effect for patient within treatment group, and Baseline NSFS as covariate. An unstructured covariance matrix will be used to model the covariance of within-patient scores. The Kenward-Roger approximation will be used to estimate denominator degrees of freedom. Comparison against placebo will be performed with the MIN-101 64 mg and 32 mg doses.

The hypotheses can be expressed as follows:

```
Null Hypothesis (H_0): \muMIN-101 64 mg - \muControl = 0 and \muMIN-101 32 mg - \muControl = 0
```

Alternative Hypothesis (Ha):  $\mu$ MIN-101 64 mg -  $\mu$ Control  $\neq$  0 or  $\mu$ MIN-101 32 mg -  $\mu$ Control  $\neq$  0

where  $\mu$ MIN-101 64 mg and  $\mu$ MIN-101 32 mg refer to the mean change from Baseline to week 12 in the PANSS Marder NSFS score at each of the 2 experimental doses, and  $\mu$ Control refers to the mean change from Baseline to week 12 in the PANSS Marder NSFS score in the placebo arm.

As described in Section 3.3.3.1, the adjustment for multiplicity within the family of primary hypotheses will utilize the truncated Hochberg procedure for the purpose of reporting results. This procedure will allow the null hypothesis of no treatment difference for both the 64 mg and 32 mg doses versus placebo to be rejected if largest p-value of comparing either of these 2 doses versus placebo is at or below 0.05. Otherwise, the lowest of these 2 p-values must be at or below 0.025 reject the null hypothesis for the representative dose.

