#### 5.2.6. Additional Analyses of the Key Secondary Endpoint

[figure not shown]
The key secondary analysis will be repeated under several subgroups. Subgroup analyses include age groups (cutoff based on tripartite), BMI ( $\leq$  median vs. > median), and history of use of specific antipsychotic medication (no treatment since screening vs. long-acting treatment vs. oral treatment only).

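### SAP 3.3.2 says no subgroup analyses are planned, but 5.2.3 and 5.2.6 repeat the NSFS and PSP analyses in eight subgroups, with no visible interaction test, exploratory label or rule on whether Hochberg and the PSP gate apply

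*SAP*

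**What the plan says.** Section 3.3.2 of the SAP is a single sentence: "At present no analyses are planned to examine study results within patient subsets".

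Section 5.2.3 then says of the primary endpoint: "The primary analysis will be repeated under several subgroups". Section 5.2.6 says of PSP: "The key secondary analysis will be repeated under several subgroups". The first two factors are given as "Subgroup analyses include age groups (cutoff based on tripartite), BMI (≤ median vs. > median". The third is antipsychotic history, with levels "no treatment since screening vs. long-acting injectable treatment vs. oral treatment only" (5.2.6 words the middle level slightly differently). The output list in Section 9.1 includes PSP tables for all three factors.

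The analysis being repeated is the MMRM of Section 5.2.2, or 5.2.5 for PSP, in which "Comparison against placebo will be performed with the MIN-101 64 mg and 32 mg doses". Section 5 sets the default: "All statistical testing will be two-sided and will be performed using a significance (alpha) level of 0.050 unless stated otherwise". Section 5.2 says of efficacy: "All statistical tests will be 2-sided hypothesis tests performed at the 5% level of significance".

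Section 3.3.3 limits study-wise error control to the primary and key secondary comparisons. Sections 5.2.2 and 5.2.5 contain the Hochberg rule, and 5.2.5 evaluates PSP only if both primary comparisons succeed. Neither 5.2.3 nor 5.2.6 says whether these rules follow the analysis into the subgroups.

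**The concern.** There are two faults, and they compound each other.

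The first is the contradiction. The same SAP can be cited to call a subgroup result pre-specified (5.2.3, 5.2.6) or unplanned (3.3.2), so its status could be argued after the data are seen.

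The second is the method. The purpose of a subgroup analysis is to ask whether the treatment effect differs between groups. A separate test in each group does not answer that. A significant result in one group beside a non-significant result in another is compatible with identical effects. The test that addresses the question is the treatment-by-subgroup interaction, and none is planned in the visible text.

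Two misreadings follow. If the drug does nothing, a subgroup may reach nominal significance by chance and be presented as a group that responds. If the drug works equally in everyone, small subgroups will often miss significance and look like groups without benefit.

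**Working it through.** **Plan's own sample size.** Inputs from SAP 3.1: difference 3, SD 6.5, two-sided 0.05, power 90%. Per arm, n = 2 × (1.960 + 1.282)² × 6.5² / 3² = 98.7, so 99 against the stated 100. Inflating for 40% non-evaluable, 100 / 0.6 = 166.7, so 167; 3 × 167 = 501. The plan's figures are reproduced.

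**Number of contrasts.** Levels: 3 + 2 + 3 = 8. Two doses versus placebo give 8 × 2 = 16 per endpoint, or 32 over NSFS and PSP.

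**Chance results with no effect anywhere.** Treating the tests as independent gives 1 − 0.95^16 = 56.0% and 1 − 0.95^32 = 80.6%. These are too high, because the contrasts share a placebo group, the three factors cut the same patients, and the two endpoints are correlated. A simulation that allows for this (8,000 trials per setting) used 100 or 167 patients per arm, history splits of equal thirds, 10/20/70% and 5/10/85%, NSFS–PSP correlation 0 to 0.7, independent factors, and t-tests standing in for the MMRM. The chance of at least one nominal result was:

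| Reading of the SAP | Either direction | Favouring drug |
|---|---|---|
| NSFS only, 16 contrasts, unadjusted | 45–48% | 24–26% |
| NSFS only, Hochberg within each subgroup | 27–29% | – |
| Both endpoints, PSP gate carried over | 45–48% | – |
| Both endpoints, Hochberg within each subgroup | 43–49% | – |
| Both endpoints, all 32 unadjusted and ungated | 64–72% | 37–45% |

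Among simulated trials whose overall NSFS test failed, 43–45% still had a nominal NSFS subgroup result, and 23–25% had one favouring drug.

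**Misses with a uniform effect at the planned size.** Standardised effect 3 / 6.5 = 0.46, 100 evaluable per arm, two-sample t-test at 5%, noncentral t:

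- Age third, 33 per arm: power 0.455. Six contrasts, expected misses 6 × 0.545 = 3.27.
- BMI half, 50 per arm: power 0.627. Four contrasts, expected misses 4 × 0.373 = 1.49.
- History in equal thirds, 33 per arm: as for age, 3.27.

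The total is 3.27 + 1.49 + 3.27 = 8.03 of 16. With a 10/20/70 history split, powers are 0.165, 0.296 and 0.774, so history misses are 2 × (0.835 + 0.704 + 0.226) = 3.53 and the total is 8.29. With 5/10/85, powers are 0.099, 0.165 and 0.849, and the total is 8.54. About half of the NSFS subgroup tests are therefore expected to miss although the effect is the same everywhere.

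**The case against.** The best defence is that these are additional analyses outside the controlled family. Section 3.3.3 confines error control to the primary and key secondary comparisons, so nothing in 5.2.3 or 5.2.6 can inflate the confirmatory error. On that view 3.3.2 is a stale sentence, as its opening words suggest, and the remedy is one line of editing. Further, what is repeated is the primary or key secondary analysis, and as defined those include Hochberg and, for PSP, the gate. Some tables and figures are missing from the public text, so statements about what is absent can only concern what is visible.

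Much of this stands. The confirmatory error is intact, and the SAP leaves the reach of Hochberg and the gate unstated; it does not remove them.

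For the same reason, three stronger readings that a reader might infer are not supported:

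- That a chance subgroup finding is more likely than not. This requires all 32 contrasts unadjusted and ungated, both endpoints pooled, and results against the drug counted. Every other reading in the table falls below 50%.
- That after a failed primary endpoint some nominal subgroup result appears about two times in three. This counts PSP tests that 5.2.5, read naturally, would not evaluate in that case.
- That the rate should be compared with the study-wise 0.05. That alpha does not cover these analyses.

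The defence does not supply an interaction test or an exploratory label. Nor does it meet the problem of misses, which does not depend on the gate, on pooling endpoints or on counting both directions.

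**Conclusion.** The point holds in a limited form. The contradiction between 3.3.2 and 5.2.3/5.2.6 is certain on the text. The visible plan would judge each subgroup by its own 5% test and never test whether subgroups differ.

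The size depends on rules that the SAP leaves open. Under no effect, the chance of a nominal NSFS result runs from 27–29% with Hochberg to 45–48% without it. Only the least restrictive reading over both endpoints reaches 64–72%. Under a uniform planned effect, roughly 8 of 16 NSFS tests miss, and one age third has about 45% power.

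These figures rest on assumptions outside the documents: tripartite read as thirds, independent subgroup factors, the history split, the NSFS–PSP correlation, and t-tests in place of the baseline-adjusted MMRM. The miss calculation uses the plan's own effect and SD. The consequence is for interpretation, not for the validity of the primary test.

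**What to change.** Replace the sentence in 3.3.2 with a statement that the subgroup analyses of NSFS and PSP in 5.2.3 and 5.2.6 are exploratory and that no efficacy claim will rest on them.

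In 5.2.3 and 5.2.6, for each factor:

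- Fit one MMRM on all patients, adding subgroup, subgroup-by-visit, treatment-by-subgroup and treatment-by-subgroup-by-visit to the existing terms.
- Report each dose-minus-placebo estimate at Week 12 with its 95% confidence interval, and the Week 12 interaction p-value, labelled exploratory and unadjusted.
- State that the 5% testing rule in 5.2 does not apply to within-subgroup comparisons. This also settles whether Hochberg and the PSP gate reach them.

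The cost is SAP wording and four added terms per factor, with no new data. The interaction tests will have low power and carry their own unadjusted multiplicity: if independent, 1 − 0.95³ = 14% for three tests on NSFS and 1 − 0.95⁶ = 27% (26.5%) for six over both endpoints. That is why they too need the exploratory label. Within-subgroup p-values would carry less emphasis, but they do not answer the subgroup question.

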#### 5.2.4. Key Secondary Estimand

The key secondary estimand is defined by the following components:

**Population**: Stable patients with schizophrenia with a predefined minimum PANSS negative symptom score before randomization.

**Endpoint**: Change in the PSP total score from Baseline to the end of Week 12.

The PSP involves four subscale domains: (a) socially useful activities, (b) personal and social relationships, (c) self-care, and (d) disturbing and aggressive behaviors. After each of these four areas is scored on an anchored Likert-type scale (0-5), raters are instructed to select a 10-point range within a 100-point scale, guided by the area scores assigned during assessment. Within the 10-point range, clinicians are instructed to select a numeric score based on their clinical judgment. The resulting final value is a single measurement from 1 to 100% of functioning.

**Measure of Intervention**: The effect of the initially randomized treatment that would have been observed had all patients remained on their treatment throughout the double-blind phase.

**Intercurrent events**: Early study discontinuation for any reason.

Summary measure: Difference in treatment means.

## 5.2.5. Key Secondary Efficacy Analysis

As noted in Section 3.3.4, no imputation of data elements will be performed for the key secondary analysis to be submitted to the US FDA. Pattern-mixture modelling imputation of missing key secondary endpoint data will be performed before conducting the key secondary endpoint analysis to submit within the EMA dossier. In both approaches, the estimand and analytic approach of using MMRM to evaluate the potential treatment effects is the same, but the data used to analyze the estimand is different between the US FDA and EMA dossiers.

The Personal and Social Performance (PSP) total score and change from Baseline will be summarized by treatment group and study visit. In addition, the trend in change from Baseline in PSP total score over the series of visit assessments will be presented graphically.

Change from Baseline to Week 12 in the PSP total score will be analyzed using a MMRM with fixed effects for treatment group (MIN-101 64 mg, MIN-101 32 mg, and placebo), region, visit, and treatment-by-visit interaction, a random effect for patient within treatment group, and Baseline PSP total score as covariate. An unstructured covariance matrix will be used to model the covariance of within-patient scores. The Kenward-Roger approximation will be used to estimate denominator degrees of freedom. Comparison against placebo will be performed with the MIN-101 64 mg and 32 mg doses.

As described in Section 3.3.3.2, the change from Baseline to Week 12 in the PSP total score will only be evaluated if both of the primary efficacy comparisons were significant. In this case the adjustment for multiplicity within the family of key secondary hypotheses will utilize the truncated Hochberg procedure for the purpose of reporting results. This procedure will allow the null hypothesis of no treatment difference for both the 64 mg and 32 mg doses versus placebo to be rejected if largest p-value of comparing either of these 2 doses versus placebo is at or below 0.05.

Otherwise, the lowest of these 2 p-values must be at or below 0.025 reject the null hypothesis for the representative dose.

Three approaches will be used to assess the sensitivity of the primary endpoint to patterns of early withdrawals or missing data as described in Section 3.3.4.2. The sensitivity analyses will implement the same analytic approach using MMRM to evaluate potential treatment effects.

Finally, a cumulative distribution function for the change from Baseline to Week 12 in the PSP total score will be presented.

[figure not shown]
#### 5.2.6. Additional Analyses of the Key Secondary Endpoint

[figure not shown]
The key secondary analysis will be repeated under several subgroups. Subgroup analyses include age groups (cutoff based on tripartite), BMI ( $\leq$  median vs. > median), and history of use of specific antipsychotic medication (no treatment since screening vs. long-acting treatment vs. oral treatment only).

## 5.2.7. Additional Secondary and Exploratory Endpoints

Other secondary and exploratory endpoints include:

- Change from Baseline in the CGI-S score
  - The CGI-S is a single Likert-type scale assessing the severity of mental illness. The scale includes 0 (not assessed), then 1 (normal, not ill at all) to 7 (among the most extremely ill patients).

## 5.2.8. Secondary and Exploratory Analyses

• Change from Baseline in the CGI-S score: CGI-S scores and change from Baseline will be summarized by treatment group and study visit. Differences between treatment groups in change from Baseline at Week 12 will be analyzed using MMRM in the same manner as the analysis of the primary endpoint.

#### 5.3. PHARMACOKINETIC/PHARMACODYNAMIC ANALYSES

## 5.3.1. Pharmacokinetic Analyses

A separate population PK analysis plan will provide details of these analyses and results of the population pharmacokinetic analysis will be presented in a separate report.

For reference, plasma concentrations will be summarized by treatment. Nominal time points will be used. The summary will include mean, standard deviation and coefficient of variation, minimum and maximum.

## 5.3.2. Pharmacokinetic / Pharmacodynamic Analyses

Exposure-response relationship by visit will be graphically explored by plotting the mean  $\pm$  SE of the plasma concentration that are sampled at the approximate time of  $C_{max}$  using the concentration exposure bins described in Table 3 (x-axis) versus change from Baseline in PANSS and PSP scores, by visit. This analysis will be performed for Marder NSFS, PSP total score, PANSS total score and subscale scores (positive symptoms, negative symptoms, general psychopathology), and the 4 remaining Marder factor scores (positive symptoms, disorganized thought, uncontrolled hostility/excitement, and anxiety/depression).

Additionally, exposure-response will be assessed by comparing differences in change from Baseline in the scales and subscales listed above between concentration exposure bins by means of a repeated measures analysis of covariance (ANCOVA) model with PK concentration bin group, gender, and visit as fixed effects, Baseline assessment value as a covariate, and subject as a random effect. Summary tables using descriptive statistics by concentration exposure bins will also be generated.

These analyses will be performed for MIN-101 plasma concentration and its main metabolites, as separate analyses.

Table 3	Concentration.	Exposure Bins
---------	----------------	---------------

PK Concentration (ng/ml)	Concentration (exposure) Bin
$> 0$ and $\le 1$ st Quartile (Q1)	A (0, Q1]
$>$ Q1 and $\leq$ Q2	B (Q1, Q2]
$>$ Q2 and $\leq$ Q3	C (Q2, Q3]
> Q3 and ≤ Q4	D (Q3, Q4]
Placebo	E (Placebo)

#### 5.4. SAFETY ANALYSES

Safety and tolerability will be analyzed for the double-blind treatment phase using the Safety Population and will be repeated for the whole study. Safety assessments include adverse events (AEs), clinical laboratory parameters, vital signs including body weight and waist circumference, ECG parameters, physical examination, Abnormal Involuntary Movement Scale (AIMS), Barnes

Akathisia Rating Scale (BARS), S-AS, and the Sheehan Suicidality Tracking Scale (Sheehan-STS), and the Readiness for Discharge Questionnaire (RDQ).

#### 5.4.1. Adverse Events

Adverse events will be mapped to a Medical Dictionary for Regulatory Activities (MedDRA) version 20.1 preferred term and system organ classification. If a patient experiences multiple events that map to a single preferred term, the greatest severity grade and strongest investigator assessment of relation to study medication will be assigned to the preferred term for the appropriate summaries. As noted in Section 3.3.4.3 and Section 3.3.4.4, should an event have a missing severity or relationship, it will be classified as having the highest severity ("severe") and/or strongest relationship to study medication ("definitely related") if it is deemed treatment-emergent.

A summary of adverse events will provide an overview of the number of patients that experienced a TEAE and the total number of TEAEs observed within those patients. Similar summary measures will be included to display the number of patients and corresponding events within events that were related to study drug, were serious, led to discontinuation of study drug, or led to death.

The occurrence of TEAEs will be summarized by treatment group using preferred term, System Organ Classification (SOC), and severity. Separate summaries of treatment-emergent serious adverse events, treatment-emergent adverse events related to study treatment, treatment-emergent adverse events leading to discontinuation of study treatment, and treatment-emergent fatal adverse events will be generated. All adverse events reported will be listed for individual patients showing both verbatim and preferred terms, as well as SOC. All adverse events that occurred prior to the initiation of study treatment will be excluded from the tables but will be included in the listings.

TEAEs of special interest will be tabulated if any are observed. Adverse events of special interest (AESI) are:

- Palpitations or abnormal heart rhythms
- · Dizziness or syncope
- Seizure

Missing onset dates will be imputed as previously outlined in Section 3.3.5 as required to determine treatment-emergent events. Adverse events occurring on Day 1 with missing onset times will be assumed to be treatment emergent.

An AE that occurs > 14 days after the date of the last dose of treatment will not be considered a TEAE but will be included in the patient data listings but not the summary tables.

Any patients that died, discontinued treatment due to a TEAE, or experienced an SAE will be listed separately.

Additionally, any SAEs occurring prior to randomization will be listed separately.

